9.3 Screening logs

Investigators should keep a record of how many patients were considered for the trial by maintaining a participant screening log. A screening log of all patients will be entered into a restricted access section of the main trial database. When at the site, logs may contain identifiable information, but this must be redacted before being sent to the CTR trial inbox ([contact]) when requested. Screening logs will be analysed according to the SEAR (Screened, Eligible, Approached, Randomised) framework (44).

9.4 Informed consent

The participant's written informed consent must be obtained using the trial Consent Form, which follows the Participant Information Sheet. The participant should be supported to understand the information about the trial and given ample opportunity to discuss it and ask questions. They should be given sufficient time after the initial invitation to participate before being asked to sign the Consent Form. Informed consent must be obtained prior to the participant undergoing procedures that are specifically for the purposes of the trial.

Consent may be taken by the PI or member of the trial team who is GCP trained, suitably qualified and experienced, and who has been delegated by the PI to undertake this activity. As consent is an ongoing process, at all follow-up points, research staff will confirm that the patient is willing to continue participating in the trial.

Participants' consent will be requested to collect NHS number and postcode to utilise NHS data for future research, and they will be asked to consent to data-linked longer-term follow-up.

Once the consent form is completed, one copy should be given to the participant, the original copy should be kept in the investigator site file and a further copy should be kept with participant's hospital notes. Please note, only when informed consent has been obtained from the participant, and they have been randomised/enrolled into the trial can they be considered a trial participant.

Patients participating in the trial may also opt to consent to participate in qualitative interviews (see Section 16.3). This is optional. If trial participants provide written consent on the EXCISE consent form to indicate their interest in participating in an interview, the participant will be provided with the separate information sheet with them describing the full details of the qualitative study.

Once potential interview participants have had time to consider the study information, potential interview participants will be asked by a delegated member of the research team tick the qualitative statement on the informed consent form or complete a consent to contact form as appropriate for trial participants or HCPs. For those that opt to consent to participate in an interview, the Qualitative researcher (QR) will be notified and participant details reviewed for sampling (site, age, gender, trial arm, surgical site). Those then sampled for interview will be contacted by the QR and sent the PIS for interviews, along with a consent form, elicitation

guidance document, diary booklet, timeline example and stamped addressed envelope. Once potential participants have had time to consider the study information the QR will contact them to discuss consent and arrange a suitable time for an interview.

Patients who are eligible for trial participation but decline to participate may opt to consent to participate in qualitative interviews. Health professionals involved in the trial may consent to participate in qualitative interviews.

After the participant has entered the trial, the investigator must remain free to give alternative treatment to that specified in the protocol, at any stage, if they feel it to be in the best interest of the participant. However, the reason for doing so should be recorded and the participant will remain within the trial for the purpose of follow up and data analysis according to the treatment option to which they were allocated. Similarly, the participant must remain free to withdraw at any time from the protocol treatment without giving reasons and without prejudicing their further treatment (see Section 13.1 or further details on Withdrawal).

9.4.1 Impaired capacity to consent

Skin cancer is associated with ageing as solar damage accumulates over the course of a lifetime (1,2). Similarly, older people are at an increased risk of developing other long-term conditions including those associated with cognitive impairment such as dementia (45). According to Alzheimer's Research UK, 1 in 6 people over the age of 80 will develop some form of dementia (46) leading to a rise in the number of older people living with comorbid cancer and dementia (47). The co-existence of these two illnesses has serious health and economic impact on patients and their families, as well as health-care systems, and there is an urgent need for treatment guidelines for this growing patient population (48).

Due to the increased prevalence of multiple long-term conditions (MLTCs) such as dementia in this patient population, the trial has been designed to include participants who lack capacity to consent. Recruiting only participants who can consent for themselves will not generate the evidence needed for this patient population (49). Where there are concerns that a potential participant may lack capacity to consent to the trial even when supported to understand the information and make a decision about participating, the site PI (or suitably qualified healthcare practitioner who has been delegated the role), will determine capacity.

In accordance with mental capacity legislation (50, 51) there is a presumption that a potential participant has capacity to consent. Where a potential participant lacks capacity to consent, participation in the trial should be discussed with friends and family who may be willing to act as their personal legal representative – in accordance with the Medicines for Human Use (Clinical Trials) Regulations, 2004 (52) this is a person who, by virtue of their relationship, is suitable to act as their legal representative and is available and willing to act. An Information Sheet and Consent Form for Legal Representative will be provided, and they will be asked to

provide informed consent that represents the person's presumed will. If there is any indication that the participant in any way objects, they will not be recruited. In accordance with the Medicines for Human Use (Clinical Trials) Regulations, 2004 (52), the interests of the patient will always prevail over those of the trial.

Given the short duration of the trial, it is unlikely that a participant who gives informed consent at the outset will subsequently lose capacity. However, should this occur, the participant's initial consent to participate in the trial, given while capable, remains legally valid according to the Medicines for Human Use (Clinical Trials) Regulations, 2004 (52). The participant will remain in the trial unless it becomes apparent that continued participation is not in the best interests of the participant (for medical or other reasons) or if there is any indication that the participant would object to continued participation (based on previous known wishes or any expression of distress or objection), as outlined in the Mental Capacity Act, 2005. This approach is outlined in the participant information sheet and consent form.

Where it is suspected that the participant lacks capacity to continue to consent and the protocol is changed or additional consent is required from participants, then a family member or friend will be approached to act as their personal legal representative (e.g. the support person outlined in 9.4.1). If the participant does not consent to consulting their legal representative upon losing capacity, or it is not possible to contact their personal legal representative, the participant should be fully withdrawn if the protocol is changed, or additional consent is required from participants. Any request made by a personal legal representative to withdraw a participant from the trial, even if outside of the above conditions, should be considered. If the participant themselves raises any objections, their withdrawal will be processed.

If their personal legal representative declines, the participant should be fully withdrawn from the trial. In the event of a suspected SSI, participants will still be asked to report to their site for treatment.

Given the short duration of the trial, we do not anticipate that a participant who lacks capacity at the outset due to pre-existing cognitive impairment would regain capacity during the trial.

9.5 Registration and Randomisation

9.5.1 Registration

After consent and prior to randomisation, the participant will be registered on the EXCISE web-based system and assigned a unique trial primary identifier (ID). Following registration, sites will complete the screening and baseline assessments including medical history, surgical and drug history using the electronic screening CRF on the trial database.

9.5.2 Randomisation

We will randomise 380 participants between the two groups (190 participants per group) with a 1:1 allocation ratio. Randomisation will occur electronically prior to surgery. Allocations will be minimised (with random element) by SSI risk associated with reconstruction method (primary closure, skin graft or local skin flap) and anatomical site (below knee or other anatomical site) and stratified by the recruitment site.

A computerised web-based remote randomisation system will be used. The Trial Manager will also be notified that a participant has been randomised via an automated email alert mechanism to the EXCISE email inbox. This system will be maintained by the Cardiff Centre for Trials Research (CTR) and accessed by the local investigator, or site staff delegated to do so, following consent and completion of baseline assessments. In the event the online randomisation system is unavailable at site, or the site has problems accessing the online website, participants will not be disadvantaged by having their surgery delayed and will be excluded from the trial.

10 Trial Intervention

Participants will be randomised in a 1:1 ratio to receive placebo or the following treatment, which is considered as an IMP within this trial:

- Oral flucloxacillin capsules
- Placebo comprising of all excipients of the active IMP except for the absence of the active ingredients

10.1 Treatment

1g dose (500mg x 2 capsules) of pre-operative oral flucloxacillin/placebo (as per randomisation).

The Summary Product Characteristics (SmPC) for Flucloxacillin (dated 17-Sep-2024 as updated by electronic medicines compendium (eMC)) made by Flamingo Pharma (UK) Ltd will be used as the RSI.

10.2 Treatment supply and storage

Oral flucloxacillin capsules and placebo will be procured and subsequently over encapsulated, packed, labelled and numbered as per the randomisation list (provided by CTR) by SIMBEC-ORION. SIMBEC-ORION is a licensed facility meeting Good Manufacturing Practice (GMP) standards. Labelling will contain the information from Annex 13 of the Labelling Regulations. The flucloxacillin will be sourced from any manufacturer which holds a valid Marketing Authorisation (MA) for the product. The SmPC detailed below for flucloxacillin is manufactured by Flamingo pharma and is representative of the product that is going to be administered.

These medicinal products do not require any special storage conditions, below 25°C, they are stable with a long shelf life under standard conditions (room temperature/below 25°C) therefore, IMP storage temperature will not be monitored in this trial consistent with Type A clinical trials.

Trial medication packs will be released by a Qualified Person to be distributed to recruiting centres and stored in pharmacy or in designated medicine cabinets within clinical areas, whichever is standard practice at the recruiting NHS Trust/Health Board. The trial medication is for trial participants' use only and will be stored separately from NHS medications.

10.3 Treatment prescribing and dispensing

The trial medication will be dispensed by the site trial team before surgery, which reflects current standard UK practice. The IMP will be prescribed by a doctor/ nurse delegated to do so on a trial-specific prescription which will be kept on file by the research nurse for IMP accountability specifying the pack ID to be dispensed. Further guidance on IMP management and supply will be detailed in the trial specific IMP Handling Manual and provided to study sites.

10.4 Dose modification for toxicity

The IMP is a one off pre-operative treatment and will be administered prior to surgery. Dose modification is not permitted.

10.5 Management of toxicity and hypersensitivity reactions

Patients should be evaluated for history or risk of hypersensitivity to the active substance, to any of the ingredients listed in section 6.1 of the SMPC, or to β -lactam antibiotics (e.g. penicillins, cephalosporins). Flucloxacillin is contra-indicated in patients with a previous history of Flucloxacillin-associated jaundice/hepatic dysfunction. Participants with previous allergic reaction to penicillin will for this reason be excluded from the trial. Participants who experience signs of post-administration reactions should be managed as per local NHS guidance and any suspected reactions should be reported to the CTR.

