- A copy of the most recent approved GP letter on host care organisation headed paper.
- Returned copy of the Source Data Agreement signed by the PI.
- Pharmacy confirmation that they have received the first shipment of IMP prior to opening the site. N.B. This is not a regulatory requirement more good practice.

Upon receipt of all the above documents, the Trial Manager will send written confirmation to the Principal Investigator/lead Research Nurse detailing that the centre is now ready to recruit participants into the trial. This letter/email must be filed in each site's Site File. Along with the written confirmation, the site should receive their trial drug supplies and a trial pack holding all the documents required to recruit into the Trial.

Occasionally during the trial, amendments may be made to the trial documentation listed above. CTR will issue the site with the latest version of the documents as soon as they become available. It is the responsibility of

the CTR to ensure that they obtain local R&D approval for the new documents. Site initiation will be by an online meeting.

The Trial Management Group (TMG) will apply for the trial to be registered with the Associate PI (API) scheme run by NIHR and will encourage the PI at each site to recruit a healthcare professional early in their research career to consider registering with the scheme.

8 Participant selection

Participants are eligible for the trial if they meet all of the following inclusion criteria and none of the exclusion criteria apply. All queries about participant eligibility should be directed to the Trial Manager before randomisation/registration. Sites are encouraged to recruit a broad range of participants, including with respect to ethnic diversity, socio-economic status, digital/health literacy and age.

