8.2 Exclusion criteria

- 1) Clinical evidence of skin cancer infection at baseline using CDC criteria.
- 2) Skin tumour removal planned with curettage, Mohs micrographic surgery/ margin-controlled excision or shave excision.
- 3) Wound left for delayed reconstruction or secondary intention healing or closed with dermal substitute.
- 4) Concurrent oral antibiotic treatment (<24 hours after last dose).
- 5) Documented poor renal function (creatinine clearance < 10ml/min).
- 6) Previous allergic reaction to penicillin.

9 Recruitment, Screening and registration

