9.2 Participant identification

Potential participants will be identified through the NHS care pathway during their initial consultation for their skin cancer excision. Once a patient has been identified as potentially eligible to participate, the opportunity will be discussed with the patients, and they will be given a copy of the trial PIS and ICF. The patient will be given adequate time to consider the trial and given the opportunity to ask further questions.

Our feasibility study, OASIS (24) showed that the average age of patients in this study population was 77 years old. We have designed the trial in line with best practice recommendations for research involving older people (42) and developed our patient facing materials using the NIHR INCLUDE Impaired Capacity to Consent Framework to ensure accessibility of the trial for those with cognitive and other impairments (43).

Information will be provided in a range of materials and formats such as large print versions, summary information sheets, and an infographic recruitment video, developed in consultation with our PPI representatives to ensure the information is accessible, including those with cognitive and/or communication impairments such as poor vision.

Participants should be encouraged to discuss the trial with their friends and family if they wish who can support them to decide about participating and/or support them to take part.

The right of the participant to refuse to participate in the trial without giving reasons must be respected. However eligible participants who refuse to participate will be approached to ask for their reason following the SEAR framework for monitoring recruitment and inclusivity (44).

The PI or nominated delegate listed on the trial delegation log must confirm eligibility of a patient in the patient's medical notes and by completing the Eligibility checklist prior to enrolment. Randomisation will only be possible once the patient's eligibility is confirmed.

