10.10 Compliance

Participants will receive a one-off dose of either flucloxacillin or placebo after informed consent is received, after randomisation and prior to surgery. The research nurse or delegated site staff will confirm participant has received the intervention by recording on the accountability logs and completing the CRF.

11 Trial procedures

Table 2 below summarises the trial procedures, which will be performed at each visit by the PI or those delegated to do so. Individual trial procedures are described in detail below.

Surgical Procedures

Following randomisation, oral flucloxacillin capsules or placebo will be dispensed by the trial team before surgery, and complete accountability logs according to the IMP Handling manual.

We will recommend adherence to the WHO guidelines for reducing SSI for surgical excision and wound closure (53,54):

Standard preparation of the surgeon including surgical scrub/ alcohol gel and sterile gloves ± gown

- Alcoholic chlorhexidine skin preparation, except where this is contraindicated (such as the face or ears,
 or around mucous membranes) where an aqueous solution should be used), or aqueous povidoneiodine if both an alcohol-based solution and chlorhexidine are unsuitable.
- Absorbable or non-absorbable sutures may be used.
- Skin glue should not be applied to the wound.
- Simple (non-active) dressings should be applied post-operatively, with or without steri-strips, except where this is impractical (such as around the eyes, ear or mouth).

We will monitor adherence with WHO guidelines using a post-surgery specific Case Report Form.

Post Surgical Care Procedures

We will standardise wound care advice and all participants will be advised to contact their local recruiting centre if they have any concern about SSI to arrange a face-to-face clinical review. Outcomes will be assessed by HCPs blinded to allocation.

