15.7 Inclusion in analysis

This analysis will include all randomised participants regardless of intervention receipt (as we will be using a treatment policy strategy for handling this intercurrent events).

16 Analysis

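### Section 10.5 names a hepatic contraindication to flucloxacillin that the exclusion criteria omit, so a patient with that history is eligible as written

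*Protocol*

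**What the plan says.** Protocol section 10.5 (Management of toxicity and hypersensitivity reactions) gives the contraindication without qualification: "Flucloxacillin is contra-indicated in patients with a previous history of Flucloxacillin-associated jaundice/hepatic dysfunction". The sentence that follows turns a different risk into an exclusion: "Participants with previous allergic reaction to penicillin will for this reason be excluded from the trial".

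Section 8.2 has six exclusion criteria, and the synopsis has the same six. In short they are: infection of the lesion at baseline; removal by curettage, Mohs or other margin-controlled surgery, or shave; a wound left open, reconstructed later or closed with dermal substitute; current or very recent oral antibiotics; creatinine clearance below 10 ml/min; and, last, "Previous allergic reaction to penicillin".

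The status of these lists is fixed in section 8: "Participants are eligible for the trial if they meet all of the following inclusion criteria and none of the exclusion criteria apply". Section 9.2 then sets the step to allocation: "Randomisation will only be possible once the patient's eligibility is confirmed". Section 11 (Surgical Procedures) gives the order of events after that: "Following randomisation, oral flucloxacillin capsules or placebo will be dispensed by the trial team before surgery".

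**The concern.** The protocol says the study drug must not be given to a certain group of patients, yet its eligibility rule lets them in. A site that applies the lists exactly as written reaches the wrong answer for such a patient.

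The main stake is safety. Treatment is one dose before surgery, so once it has been swallowed there is nothing left to stop. Earlier exposure to flucloxacillin is plausible in this population: section 4.1 describes it as the first-choice oral antibiotic for skin infection in the UK, and section 4 says it is commonly prescribed for this type of surgery. The feasibility cohort had an average age of 77 (section 9.2), and section 9.4.1 deliberately admits people who lack capacity. Recall of an old drug reaction may be less reliable in such patients, so an explicit prompt at screening would be useful.

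A lesser stake is that a patient whose history comes to light only when the drug is dispensed has already been randomised and remains in the primary analysis without treatment.

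**Working it through.** The protocol has no figure on this point to reproduce. The check compares texts, with one illustrative calculation of scale.

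**Step 1. Compare the contraindication with the exclusion lists.**

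| Item in 8.2 and synopsis | Covers earlier flucloxacillin-associated jaundice or hepatic dysfunction? |
|---|---|
| 1. Lesion infection at baseline | No |
| 2. Curettage, Mohs/margin-controlled or shave removal | No |
| 3. Delayed or secondary-intention healing, or dermal substitute | No |
| 4. Concurrent oral antibiotics | No |
| 5. Creatinine clearance below 10 ml/min | No (renal only) |
| 6. Penicillin allergy | Not on its face: drug-associated jaundice is not described as an allergic reaction |

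None of the six covers it, and neither list has a general item excluding patients with any contraindication in the product information.

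**Step 2. Look for another rule that closes the gap.**

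- Section 10.5 asks sites to evaluate history or risk of hypersensitivity. It does not ask them to evaluate hepatic history or exclude on it.
- Section 10.8 refers to the SmPC, but only for concomitant medicines and interactions.
- Sections 9.5.1 and 11.1 require medical and drug history at baseline, but do not name this history or say what follows if it is found.
- Section 10.3 has a delegated doctor or nurse prescribe, which comes after eligibility has been decided.
- Section 13.1 allows withdrawal when enrolment was inappropriate, which comes after enrolment.

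No section turns the contraindication into a condition for entry.

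**Step 3. Follow such a patient through.** The lists are met, so eligibility can be confirmed (sections 8 and 9.2) and the patient can be randomised 1:1 (section 9.5.2). Dispensing follows. If the dose is withheld at that stage, section 15.7 still applies: "This analysis will include all randomised participants regardless of intervention receipt".

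**Step 4. Scale.** Inputs from section 15.3: 380 randomised, 190 per group. The prevalence *p* of this history among otherwise eligible patients is not in the protocol; the range below is an assumption for illustration. Expected number = n × p.

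| Assumed p | Randomised: 380 × p | Allocated flucloxacillin: 190 × p |
|---|---|---|
| 1 in 10,000 | 0.038 | 0.019 |
| 1 in 1,000 | 0.38 | 0.19 |

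These are expected numbers before any clinician stops the dose.

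**The case against.** The strongest reply is that the protocol does not permit this dosing; it only fails to repeat the bar in the list. The contraindication is printed in the treatment section, and the trial must be run in compliance with the protocol. Screening is also substantial: section 11.1 says the baseline assessments, including full medical history, serve to determine eligibility; section 9.5.2 puts randomisation after baseline assessments; and Table 2 gives the eligibility assessment to a qualified medical professional. The usual point of detection is therefore before randomisation. The eligibility checklist and the IMP Handling Manual are not available here and may already carry the item. Section 8.2 also does not try to list every prescribing check: excipient and cephalosporin hypersensitivity are mentioned in 10.5 without a matching exclusion.

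Much of this stands as mitigation. A careful prescriber would probably catch such a patient, and it would be too strong to say the dose is prevented by unaided judgement when the warning is in print. Keeping one undosed patient in the analysis is what a treatment-policy strategy intends, and one in 380 is immaterial.

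The gap remains, however. None of these safeguards tells staff to ask about this history or to exclude on it, and section 8 makes the lists decisive. Hypersensitivity to excipients or cephalosporins is put in 10.5 as something to evaluate, whereas the hepatic history is called a contraindication outright. A checklist that nobody outside the trial team can see does not correct the protocol's own eligibility rule.

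**Conclusion.** The concern holds. Section 10.5 and the exclusion lists are inconsistent, and following the stated eligibility rule admits a patient for whom the protocol itself calls the drug contraindicated. It reads as an omission rather than a choice, because 10.5 carries one risk forward into an exclusion and leaves the other behind.

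The size is probably very small: well under one expected patient in the whole trial over the assumed prevalence range. There is no effect on sample size, alpha or power, and no material effect on the primary analysis. It should be fixed on grounds of patient safety and internal consistency. The conclusion rests only on the protocol's own statement of the contraindication; the SmPC was not consulted. Confidence is high about the omission. How often it would lead to a contraindicated dose cannot be judged from the protocol.

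**What to change.** Add a seventh exclusion criterion to section 8.2 and the synopsis: previous flucloxacillin-associated jaundice or hepatic dysfunction. Extend the sentence in 10.5 that excludes penicillin-allergic patients so that it names this group too. Confirm that the eligibility checklist asks about this history, so that it is screened before randomisation rather than at dispensing.

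The cost is a few lines of text, a check of one form and the effort of an amendment. The loss of eligible patients is negligible, and no statistical quantity needs to be recalculated.
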